### 8.1 **CZP** plasma concentrations

Only CZP plasma results analyzed using the ECLIA method will be summarized using the participants in the PK-PP set. CZP plasma concentrations are measured at Baseline, Weeks 1, 4, 12, 16, 17, 24, 32, 40, 48, every 24 weeks thereafter, the Early Discontinuation/EOT Visit, and the Final Visit; for study participants enrolled prior to Protocol Amendment 8, samples were not collected after implementation of Protocol Amendment 8. CZP plasma concentrations will be summarized by CZP dose (Original CZP Dose, Reduced CZP Dose) using geometric means, 95% CIs for the geometric mean, geometric CV, and the median, minimum and maximum concentrations.

The geometric CV will be calculated using the following formula:

$$geoCV(\%) = \sqrt{\exp(SD^2) - 1} * 100$$

where SD=standard deviation from the log-transformed data.

For the two CZP Dose groups, summaries at all available visits and plots of plasma concentration results will be produced separately by Baseline weight group, Baseline age group, ADAb participant status classification, ADAb titer classification (see Section 8.2) and, concomitant MTX use in combination with Baseline weight group.

Line-plots will be produced to summarize geometric mean (+/- 95% CI) plasma concentration over time. On each plot there will be separate plot lines for each subgroup category as described above. Plasma concentration will be plotted on both linear and semi-logarithmic scales.

In addition, spaghetti plots of CZP plasma concentrations over time will be produced for individual study participants, separately for each CZP dose group. Plots will be provided by Baseline age group, Baseline weight group, concomitant MTX use in combination with Baseline weight group. In each plot, different symbols/colors will be used to identify subgroup categories.

Concentrations below the limit of quantification of 320.0 ng/mL (0.32µg/mL) (BLQ) will be replaced by the LLOO divided by 2 for the calculation of descriptive statistics. The geometric

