## 8.2 Anti-CZP antibodies

Immunogenicity will be assessed through listing of individual results by study participant and summary tables and graphs for data generated with the ECLIA method only for the SS. Immunogenicity data will be related to PK (using the PK-PP set), efficacy (using the FAS) and safety (using the SS). All data including those results at the Final Visit will be used for analyses for the entire study.

Anti-drug antibodies will be assessed by a three-tiered approach: screening (positive or negative screen), confirmatory (positive or negative immuno-depletion) and titer assays, using ECLIA methods. Cut points will be determined during assay validation and used by the bioanalytical laboratory to determine the status of ADAb in the test samples as described in Table 8–1.

Table 8-1: ADAb status at sample level

	ADAb positive	Sample values that are 'positive screen' and 'positive immuno-			
	(ADAb+)	depletion.'			
	100 V				
	ADAb negative	Sample values that are either 'negative screen' or 'positive screen' and			
	(ADAb-)	'negative immuno-depletion' if corresponding drug levels are equal or			
	, Co.	below the validated drug tolerance limit of the assay allowing detection			
	o'll'	of 100 ng/ml ADAb positive control or limit dictated by the ADAb assay			
9		and project needs (e.g. 250 ng/ml positive control).			
	ADAb negative	Sample values that are either 'negative screen' or 'positive screen' a 'negative immuno-depletion' if corresponding drug levels are equal below the validated drug tolerance limit of the assay allowing detection of 100 ng/ml ADAb positive control or limit dictated by the ADAb assay			

Table 8–1: ADAb status at sample level

ADAb inconclusive	Sample values that are either 'negative screen' or 'positive screen' and 'negative immuno-depletion' but with corresponding drug levels above the validated drug tolerance limit of the assay allowing detection of 100 ng/ml ADAb positive control or limit dictated by the ADAb assay and project needs (e.g. 250 ng/ml positive control).
Missing	Samples that were not collected per schedule or that could not be tested for ADAb status due to inadequate sample volume, mishandling, or errors in sample collection, processing, storage, etc.

Confirmed positive samples will be titrated and the titer will be reported including the minimum required dilution (MRD) of the assay.

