## 8.2.1 Participant ADAb classification

Study participants from the SS will be classified based on their baseline and treatment-emergent ADAb status (Table 8–2). Classification will be done separately for two time periods of interest: (1) using the study participants' data for the entire study treatment period and (2) using the study participants' data up to and including Week 24 (to facilitate comparison with adult RA data from study RA0138 in the Updated Week 24 Interim Analysis). Baseline ADAb values are defined as the latest (not missing, not inconclusive) measurements up to and including the date of administration of first CZP treatment.

Table 8–2: ADAb status classification at participant level

	1.	Baseline ADAb negative and treatment-emergent ADAb negative	Study participants who were negative at Baseline and negative at all sampling points post treatment until the time point of interest
71	nerit c	Bulling	Note: study participants with Baseline samples missing and negative ADAb status at all sampling points post treatment are included in this category because participants who are pre ADAb positive are expected to have ADAb positive samples post-dosing.

Table 8-2: ADAb status classification at participant level

2.	Baseline ADAb negative and treatment-emergent induced ADAb positive	Study participants who were negative at Baseline and positive at any sampling point post treatment until the timepoint of interest. This group also included study participants who had a missing Baseline sample with 1 or more positive post treatment samples.
3.	Baseline ADAb positive and treatment-emergent reduced ADAb negative	Study participants who were positive at Baseline and negative at all sampling points post treatment until the timepoint of interest.
4.	Baseline ADAb positive and treatment-emergent unaffected ADAb positive	Study participants who were positive at Baseline and were positive at any sampling point post treatment until the timepoint of interest with all titer values of the same magnitude as Baseline (i.e., less than or equal to a predefined fold increase from the Baseline value of 2.10 which is defined with the validation of the assay).

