5.	Baseline ADAb positive and treatment-emergent boosted ADAb positive	Study participants who were positive at Baseline and were positive at any sampling point post treatment until the timepoint of interest with any increased titer values compared to Baseline (greater than a predefined fold increase of 2.10 from Baseline value which is defined within the validation of the assay).
6.	ADAb inconclusive	Study participants who were positive at Baseline and some post-treatment samples until the timepoint of interest were missing or inconclusive, while other post-treatment samples until the timepoint of interest were negative.  Note: study participants who were positive at Baseline and all post-treatment samples up to the timepoint of interest were missing or inconclusive are also included in this category.
7.	Treatment emergent ADAb positive	Study participants that were classified as 2 or 5.
8.	Baseline treatment ADAb positive	Study participants who are positive ADAb at baseline, so those classified as 3, 4, 5 or 6.
9.	Missing USE	Study participants who were negative at Baseline or missing their Baseline assessment, were not positive at any post-Baseline visit, and have at least one missing/or inconclusive post-treatment scheduled assessment (until the timepoint of interest).
10	ADAb positive	Study participants who have a positive ADAb sample status at any timepoint (either Baseline or post dose).

Unscheduled visits including early discontinuation visits (ED) or Final visits with missing results are disregarded. Thus, study participants who had missing ADAb measurements at ED but were ADAb negative at all other post-treatment visits will be classified in category 1

Confidential Page 49 of 252

above. Study participants who were negative at Baseline or missing their Baseline assessment and whose only post-treatment ADAb assessment was at ED and was missing will be classified in category 9 above. Study participants who were positive at Baseline and whose only post-treatment assessment was at ED and was missing will be classified in category 6 above. Only positive data at unscheduled visits will be used for classification.

Table 8-3:	Aid to Programming	ADAb partici	pant status category

ADAb Participant Status Category	Post-Treatment ADAb Sample Status a		ample Status a
Baseline ADAb Sample Status	Any Positive	All Scheduled Negative	Some/All Scheduled Missing b
Missing	2	1	9
Negative	2	1 , 1	9
Positive	4 or 5 c	3	6

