## 8.2.2 ADAb Titer Classification

To further evaluate the impact of ADAb on PK, efficacy and safety, grouped ADAb titer categories will be defined based on ADAb quartiles (see Section 4.7) observed in the study. Quartiles will be calculated separately for the entire treatment period, and then for the period up to and including Week 24, using each study participant's highest post-treatment ADAb titer (ADAb negative participants will be deemed to have zero titer levels for calculation purposes). If all post-baseline scheduled visit results are Negative, then the study participant will be assigned to the lowest titer classification (lowest quartile); unscheduled visits with missing results are disregarded. If a study participant doesn't have any positive results at post-baseline scheduled visits and any of the results at scheduled visits are deemed missing or inconclusive, then the study participant will be assigned to "Missing".

If interpretation of the grouped titer summaries is inconclusive or results from other studies suggest other groupings, additional post-hoc analyses may be conducted to further investigate.

Immunogenicity will be assessed through summary tables and figures and listing of individual results by study participant on the SS. Summaries will be by CZP dose (Reduced

<sup>b And no positive ADAb samples post-treatment (including positive in either scheduled or unscheduled).

<sup>c Highest ADAb titer used to determine category.

CZP Dose, Original CZP Dose) and each of Baseline weight group, Baseline age group, and concomitant MTX use, unless specified otherwise.

- Number and percentage of study participants with positive, negative, inconclusive or missing ADAb sample status (Table 8–1) will be summarized at each visit and overall and by dose (Original CZP dose, Reduced CZP Dose).

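### The strictly ADAb-negative class is truncated at the assay's drug tolerance limit, so comparisons of CZP concentration and PedACR by ADAb class may understate or reverse an antibody effect

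*SAP*

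**What the plan says.** Table 8-1 (Section 8.2) puts a drug-level condition on a negative sample but none on a positive one. A negative screen, or a positive screen with negative immuno-depletion, counts as negative only if CZP is at or below the tolerance limit. The same assay result is inconclusive when it comes "but with corresponding drug levels above the validated drug tolerance limit of the assay". The limit is tied to detecting a 100 ng/ml positive control, or to another limit set by the assay and project needs. No CZP concentration is given.

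Table 8-2 (Section 8.2.1) defines category 1 as "Study participants who were negative at Baseline and negative at all sampling points post treatment until the time point of interest", and also admits children with a missing Baseline whose post-treatment samples are all negative. Category 9, 'Missing', takes children who were negative or missing at Baseline, were never positive afterwards, and "have at least one missing/or inconclusive post-treatment scheduled assessment". Any positive sample overrides missing ones. Baseline-positive children without a later positive go to category 6 if samples are missing or inconclusive. Among unscheduled samples, only positives count.

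Section 8.2.2 applies the same logic to titer. A child with no positive scheduled result goes to 'Missing' instead of the lowest class if "any of the results at scheduled visits are deemed missing or inconclusive". The treatment-emergent incidence denominator leaves out inconclusive and missing children.

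Section 8.1 summarises and plots CZP concentration by participant status and by titer class. Sections 10, 10.2 and 10.3.1 tabulate PedACR by titer class.

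**The concern.** Category 1 requires every scheduled sample to be negative, and each negative requires CZP at or below the limit. No scheduled concentration in that class can therefore exceed the limit. A child without antibody but with one higher level leaves the class. ADAb-positive children face no explicit cap. The group against which a reader will judge the positives is thus selected on the PK outcome itself, and for PedACR on its likely mediator. If antibody lowers exposure, the difference is shrunk and can change sign.

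The 'Missing' row does not reveal this, because it pools children with too much drug and children whose samples were lost or too small. The small samples matter here because archived samples were re-assayed by ECLIA only where volume sufficed.

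The incidence denominator loses the same children, which raises apparent incidence. If exposure is higher on the Original dose, it raises it more there.

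**Working it through.** The SAP states no figure on this point, so there is nothing to reproduce. Its rules were applied to simulated children.

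**From the SAP.** Post-Baseline PK samples at Weeks 1, 4, 12, 16, 17 and 24 (6 to Week 24), plus Weeks 32, 40 and 48 (9 to Week 48), from Section 8.1; the classification rules above; Reduced doses 50% of Original (Section 3.7).

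**Assumed.** ADAb samples paired with PK samples (current Section 8.2 gives no ADAb schedule); log-normal, stationary CZP levels; between-child CV 40% and within-child CV 25%; true positive/negative ratio 0.70; no antibody missed above the limit.

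**Method** (400,000 antibody-free children). Log-SD = √ln(1+CV²), giving 0.385 between and 0.246 within, total √(0.148+0.061) = 0.457. A child stays in category 1 if the largest of the 6 levels is at or below limit T. Let g be the Week 16 geometric mean of those kept divided by that of all antibody-free children. Apparent ratio = 0.70/g.

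| T, percentile | T, multiple of median | kept in category 1 | g | apparent ratio |
|---|---|---|---|---|
| 50th | 1.0 | 23% | 0.603 | 1.16 |
| 75th | 1.4 | 50% | 0.737 | 0.95 |
| 90th | 1.8 | 75% | 0.849 | 0.82 |
| 95th | 2.1 | 86% | 0.904 | 0.77 |
| 99th | 2.9 | 96% | 0.970 | 0.72 |
| – | 4.1 | >99% | 0.995 | 0.70 |

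The multiples follow from exp(z × 0.457); for the 95th percentile, exp(1.645 × 0.457) = 2.1. With 9 samples the first four ratios are about 1.2, 0.98, 0.84 and 0.79. With CVs of 50% and 30% (6 samples) the ratio is 1.30 at the 50th percentile and 0.79 at the 95th.

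**Response and incidence.** A second model used log-SDs 0.4 and 0.3, true ratio 0.50, half the children truly ADAb positive, 6 samples, and response logistic in log CZP (odds 3:1 at the median, slope 1).

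- T at the median: 80% of negatives go to 'Missing'. Response reads 59% against 63%, instead of 59% against 74%. Incidence reads 0.5/(0.5 + 0.5 × 0.197) = 84% instead of 50%.
- T at twice the median: 24% go to 'Missing', and incidence reads 57%.
- T at three times: 5% go to 'Missing', and incidence reads about 51%.
- T at five times: no visible bias.

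If exposure is dose-proportional, a limit at twice the Reduced-dose median is the Original-dose median. The same true 50% incidence would then read 57% on Reduced and 84% on Original.

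**Not modelled.** Original loading doses are twice the maintenance dose (Table 2-3), and the Week 17 sample is taken 4 to 10 days after the Week 16 dose (Section 3.5.1.1). If ADAb is sampled at those visits, one early high level removes a child for the whole period.

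**The case against.** A reader might infer that the plan hides the antibody effect outright. The documents do not support that. The limit is not stated, and at roughly three to four times the median level or above the bias is small or nil. The rule is also narrower than it may look: it concerns scheduled samples in never-positive children, any positive overrides, and Baseline-positive children have their own category 6. The lowest titer class runs up to Quartile 1, so it may also hold low-titer positives with no cap.

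A reader might also infer that the primary objective is undermined. The primary variables are CZP concentrations and ADAb levels at Weeks 16 and 48 (Section 2.2.1.1), efficacy is secondary, and Section 8.2.2 presents the effect of ADAb on PK and efficacy as a further evaluation. Everything is descriptive.

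The plan discloses something. 'Missing' is its own titer subgroup with its own PK summary, inconclusive samples are counted by visit and flagged in the individual plots, and post-hoc regrouping is allowed. This helps, but category 9 and titer class 'Missing' still mix two different kinds of child, and no planned summary returns the inconclusive ones to the negatives.

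The strongest point concerns the remedy. Leaving a result above the limit unresolved is sound assay practice, and the drug-level condition was added deliberately in SAP Amendment 4. If antibody is masked above the limit, a comparator that adds the inconclusive children absorbs undetected positives. Assume complete masking above the limit, antibody detectable at one visit, equal groups and no true effect. That comparator then gives 0.69, 0.79, 0.89 and 0.93 at the 50th, 75th, 90th and 95th percentiles, a spurious loss of exposure. The planned class errs the other way, at 1.26, 1.17, 1.10 and 1.07. This stands: the pooled group should not replace the planned one.

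**Conclusion.** The concern holds in a limited form. The strictly negative class is truncated at the tolerance limit by the SAP's own definitions, and comparisons of CZP concentration by status and titer class, and of PedACR by titer class, may therefore attenuate or reverse a true ADAb effect.

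The size cannot be fixed from the document. Under the stated assumptions it ranges from a reversal, with the limit at the median level, to nothing at about four times the median. The direction rests on antibody lowering CZP and on the pairing of ADAb with PK samples. Certain harm, or damage to a primary variable, is not shown. The change is still worth making before the final analysis, because showing both comparators lets a reader judge how far the ADAb comparison depends on the inconclusive children.

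**What to change.** 1. State in Section 8.2 the drug tolerance limit used, as a CZP concentration.
2. Split category 9 and titer class 'Missing' into (a) never positive, inconclusive because of drug level only, and (b) at least one sample truly missing. Show CZP concentrations and PedACR for each.
3. Keep category 1 and the lowest titer class as planned. Beside them, add a sensitivity comparator of negative plus drug-level-inconclusive never-positive children in the PK and efficacy displays, and use the same group in a sensitivity denominator for treatment-emergent incidence.
4. Footnote that the pooled comparator may contain undetected antibody and can itself overstate an ADAb effect, so neither comparator should be read alone.

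Cost: SAP wording, one derived flag and some extra rows. No new data are needed, and no dose or clinical rule is touched.

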- If the titer, for an ADAb level that is 'positive screen' and 'positive immunodepletion' status, is missing, then ADAb status will be considered as positive and no imputation rules apply for the missing titer.
- If the ADAb level is 'positive screen' but no confirmatory result could be determined, then a conservative approach will be used and ADAb status will be considered as positive. No imputation rules apply for the missing titer.

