## 8.2.3 Time to first occurrence of treatment-emergent ADAb positivity

Study participants will be considered to have an event at the first ADAb sampling time point with ADAb positive status in the entire treatment period if the participant is Baseline ADAb negative or first ADAb sampling time point with fold difference increase from Baseline > 2.1 if participant is Baseline ADAb positive. Study participants who are never treatmentemergent ADAb positive will be censored at the date of the last evaluable (not missing, not inconclusive) ADAb sample or on date of first CZP if no evaluable post-treatment ADAb samples. In case of Baseline ADAb positivity present in more than 10% of the study participants, the table will be produced separately for ADAb participant category 2 (induced) and 5 (boosted).

- Summary tables based on Kaplan-Meier (KM) estimates will be produced.
- Kaplan-Meier plots of time to first treatment-emergent ADAb positivity will also be produced separately for the CZP doses (Original CZP dose, Reduced CZP dose). All available data timepoints will be included.

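### Calling a screen-positive but unconfirmed ADAb sample positive is conservative after treatment but anti-conservative at Baseline, where it leaves a later positive uncountable as treatment-emergent

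*SAP*

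**What the plan says.** Section 8.2 sets a three-tier assay: screening, confirmation by immuno-depletion, then titer. Titers are planned for confirmed positives only: "Confirmed positive samples will be titrated and the titer will be reported including the" minimum required dilution. If the screen is positive and "no confirmatory result could be determined, then a conservative approach will be used and ADAb status will be considered as positive". For this case, and for a confirmed positive whose titer is missing, "no imputation rules apply for the missing titer".

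Section 8.2.1 sets the reference point: "Baseline ADAb values are defined as the latest (not missing, not inconclusive) measurements up to and including the date of administration of first CZP treatment". Treatment-emergent positive means category 2 or category 5 of Table 8-2.

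- Category 2 (induced): "Study participants who were negative at Baseline and positive at any sampling point post treatment until the timepoint of interest". It is extended to missing Baselines: "This group also included study participants who had a missing Baseline sample with 1 or more positive post treatment samples".
- Category 5 (boosted): Baseline positive and positive after treatment "with any increased titer values compared to Baseline", with a threshold of more than 2.10-fold.

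Table 8-3 gives 4 or 5 for a Baseline positive with any later positive, decided by the highest titer. In the time-to-event analysis of 8.2.3, a Baseline-positive child has an event at the "first ADAb sampling time point with fold difference increase from Baseline" above 2.1.

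**The concern.** Calling a doubtful sample positive is cautious when the question is whether a treated child has antibodies. At Baseline the label does the reverse. It raises the bar that a later positive must clear to count as treatment-emergent, and the comparison that would clear it needs a Baseline titer that does not exist.

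Immunogenicity is part of the primary objective (2.1.1). The affected outputs are the incidence of treatment-emergent ADAb, the Kaplan-Meier analysis in 8.2.3, and the prevalence of Baseline positivity. That prevalence also decides whether the 8.2.3 table is split into induced and boosted (the 10% trigger). Table 8-3 has no cell for a Baseline positive without a titer, so a programmer would have to choose the category.

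**Working it through.** **Step 1. Follow one Baseline sample through the text.** It screens positive and has no confirmatory result. Section 8.2 calls it positive. It is then neither missing nor inconclusive, so it qualifies as the Baseline value in 8.2.1. Only confirmed positives are titrated and nothing is imputed, so it has no titer.

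**Step 2. Classify by Tables 8-2 and 8-3.**

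| Post-treatment samples | Baseline missing | Baseline negative | Baseline positive, no titer |
|---|---|---|---|
| Any positive | 2, counted | 2, counted | 4 or 5, cannot be determined |
| All scheduled negative | 1 | 1 | 3 |
| Some or all scheduled missing, none positive | 9 | 9 | 6 |

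Only the first row affects the treatment-emergent numerator. There, an unconfirmed Baseline and an absent Baseline give different answers for the same later positive. If the child is put in category 4, it stays in the incidence denominator, which drops only the inconclusive and missing categories.

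**Step 3. Overlap with Table 8-1.** That table calls a sample Missing if it could not be tested for ADAb status, for example through inadequate volume. A sample with enough volume to screen but not to confirm could be read as Missing there or as positive under the rule. At Baseline, with a later positive, the first reading gives category 2 and the second gives the undetermined cell.

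**Step 4. Size.** The SAP gives no ADAb rate, so there is no figure to reproduce. All inputs are assumptions:

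- *u*: share of children whose Baseline is screen-positive without confirmation (0 to 10%), taken as truly negative and, if later positive, not counted;
- *v*: share of otherwise ADAb-negative children who become positive only through an unconfirmed post-treatment screen (0 to 10%);
- *p*: true treatment-emergent risk (20% to 95%).

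Observed rate = (1 − u) × [p + (1 − p) × v].

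Baseline effect alone (v = 0): change = −u × p, in percentage points.

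| u | p = 20% | p = 50% | p = 80% | p = 95% |
|---|---|---|---|---|
| 2% | −0.4 | −1.0 | −1.6 | −1.9 |
| 5% | −1.0 | −2.5 | −4.0 | −4.75 |
| 10% | −2.0 | −5.0 | −8.0 | −9.5 |

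Post-treatment effect alone (u = 0, v = 5%): change = (1 − p) × v = +4.0, +2.5, +1.0, +0.25 points for the same four values of p.

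Both at 5%: for p = 20%, 0.95 × (0.20 + 0.80 × 0.05) = 22.8%, or +2.8 points. For p = 50%, 80% and 95% the change is −0.1, −3.05 and −4.5 points.

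The two effects cancel when v = u × p / [(1 − u)(1 − p)]. For u = 5% that is v = 1.3%, 5.3%, 21% and 100% at the four values of p.

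**Step 5. After the change.** With an unconfirmed Baseline treated as missing, a later positive moves from the undetermined cell to category 2, and the shortfall u × p disappears. With no later positive the child moves from 3 to 1 or from 6 to 9, and the incidence does not change. The upward effect after treatment remains.

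**The case against.** The strongest objection is to a reading that this text invites: that the rule biases the immunogenicity rate downward overall. The documents do not support that. The same sentence turns unconfirmed post-treatment screens into category 2 events, and Step 4 shows that the net sign depends on three quantities the SAP does not give. Nor does the SAP say that a Baseline positive without a titer defaults to category 4. The case is undefined, so it is not established that every such child becomes a non-event.

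A reader might also infer an imbalance between doses, because Reduced-dose samples are archived and the Amendment 9 participants were assayed by ECLIA from the start. But section 2.4 records 78 participants already enrolled on the Original dose by Protocol Amendment 5, against 30 added by Amendment 9. Most of that group's samples are therefore archived too, and the argument does not carry.

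On reach, the named primary immunological variable is antibody level at Weeks 16 and 48 (2.2.1.1), not treatment-emergent incidence. There is no hypothesis testing, and individual results are listed, so affected children can be found.

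On the remedy, an unconfirmed Baseline may be a real pre-existing positive. The note to category 1 expects such children to test positive after dosing, so treating the sample as missing would count some of them as induced. That stands, and it is why a sensitivity analysis belongs with the change.

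None of this answers the narrower point: at Baseline the rule works against its stated purpose, and the tables do not classify the result.

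**Conclusion.** The point holds in limited form. The rule for unconfirmed samples is conservative after treatment and anti-conservative at Baseline. There it bars category 2, leaves category 5 and the 8.2.3 event unprovable, and treats a child with an uncertain Baseline sample less cautiously than one with none. The overlap with Missing in Table 8-1 leaves the same sample open to two readings. A confirmed Baseline positive with a missing titer meets the same gap between categories 4 and 5.

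The conclusion about the rule rests on the text alone. The sizes do not: the 1.0 to 4.75 points assume that 5% of Baselines are affected, that those samples are truly negative, and that the children are not counted. The number affected and the net direction of bias are not fixed by the document. This should be corrected before the final analysis, but it does not show that any reported rate is wrong.

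**What to change.** 1. In 8.2, limit the positive-if-unconfirmed rule to post-treatment samples, and say how it ranks against Missing in Table 8-1.
2. Treat a Baseline sample that is screen-positive without a confirmatory result as Baseline missing in Tables 8-2 and 8-3, in Baseline prevalence and in 8.2.3. The 8.2.3 text names only Baseline negative and Baseline positive, so add that a missing Baseline follows the negative branch, in line with category 2.
3. Add a sensitivity analysis that keeps such samples as Baseline positive, because some may be real pre-existing positives that the main analysis would count as induced. Report how many children are affected.
4. For a confirmed Baseline positive without a titer, state whether the child goes to category 4 or 5 and show the incidence both ways. Imputing the minimum required dilution is not advised: using the lowest reportable titer makes a 2.10-fold rise as easy as possible to reach, and it overrides the SAP's choice not to impute.

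The cost is a few sentences in 8.2, 8.2.1 and 8.2.3, a small change to the ADAb derivation, and one repeated table. No new data are needed.
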